## **1. Background**

Deep sedation during gastrointestinal endoscopy in patients with cardiopulmonary risk factors such as respective co-morbidities or also morbid obesity is challenging. Those high-risk patients are at risk of upper airway obstruction and hypoxemia. Nasal continuous positive airway pressure may help to decrease the incidence of peri-interventional hypoxemia. However, data on nasal continuous positive airway pressure in high-risk patients having gastrointestinal endoscopy are scarce; only one randomized trial on gastroscopy in obese patients is available (Kang et al. J Anesth 2021). In a very high-risk group, namely patients assessed for heart or lung transplantation in our hospital, the risk was especially high (unpublished data)

## **2. Objective**

We aim to investigate the effect of nasal continuous positive airway pressure – compared to nasal oxygen insufflation – on the incidence of hypoxemia in high-risk patients having gastrointestinal endoscopy in deep sedation.

## **3. Hypothesis**

We hypothesize that nasal continuous positive airway pressure – compared to nasal oxygen insufflation – reduces the incidence of hypoxemia in high-risk patients having gastrointestinal endoscopy in deep sedation.

## **4. Setting**

Single-centre prospective randomised trial in the Department of Interdisciplinary Endoscopy and the Department of Anesthesiology of a German university medical center.

## 5. Patients

### Inclusion criteria

- Adult and obese high-risk patients (ASA class  $\geq 3$  and/or BMI  $\geq 30 \text{ kg/m}^2$ , in accordance with the current WHO definition of obesity) scheduled for elective gastrointestinal endoscopy with deep sedation.

### Exclusion criteria

- Age  $< 18$  years
- Pregnancy
- Cognitive impairment, that makes consent to study impossible
- Known but untreated heart disease (e.g. PFO, recent congestive heart failure), complicating comparability within groups

### Outcome

#### *Primary outcome:*

- The incidence of hypoxemia defined as a peripheral oxygen saturation of  $\leq 90\%$  registered with the monitoring system of our working station (Phillips IntelliVue and Massimo Rad-97) after inducing deep sedation while under endoscopy intervention.

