#### *Secondary outcomes:*

- Duration of intervention (absolute)
- Duration of hypoxemia/Time until recovery ( $>90\%$ ) (absolute)
- Hypoxemic events per intervention
- Ratio of hypoxemia duration compared to procedure duration (relatively)
- Incidence of need for airway intervention (mask ventilation, intubation, interruption)
- Comparison between subgroups BMI 30+; 35+; 40+  $\text{kg/m}^2$

- Sedation score (Modified Observer Assessment of Alertness/Sedation)
- Continuous measurement of endtidal CO2 via the mask

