## 6. Protocol

Patients will be randomized to nasal continuous positive airway pressure or nasal oxygen insufflation.

Patients randomized to nasal continuous positive airway pressure will receive a positive pressure between 3 and 10cm H2O depending on the type of endoscopy, and an oxygen flow rate of 6l/min. Patients randomized to nasal oxygen insufflation nasal oxygen will be started with a flow of 6L/min.

Deep sedation will be performed under surveillance of an anaesthesia-team (physician and nurse) using a propofol bolus of 1 mg/kg adjusted body weight, followed by a continuous propofol infusion of 4mg/kg/h (adjusted to lean body weight) (MacDonald JJ, Moore J, Davey V, Pickering S, Dunne T. The weight debate. *J Intensive Care Soc.* 2015 Aug;16(3):234-238. doi: 10.1177/1751143714565059), until a MOAA/S Score of 1-2 is reached (Kowalski R, Mahon P, Boylan G, et al. Validity of the modified observer's assessment of alertness/sedation scale (MOAA/S) during low dose propofol sedation: 3AP6-3. *Eur J Anaesthesiol.* 2007;24:26-27, DOI:10.1097/00003643-200706001-00097). If necessary, additional boluses of 20mg Propofol will be administered until the desired sedation depth is achieved. SpO2 and heart rate will be monitored continuously. Blood pressure will be monitored using upper-arm cuff oscillometry (3-minute intervals). Additional data collected from the medical record will include baseline SpO2, post-interventional SpO2, procedure length, and length of stay in the post anesthetic care unit (PACU).

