## 7. Statistics

Descriptive analysis will be performed to describe patient characteristics and clinical data. The primary and secondary outcomes will be analysed according to the intention-to-treat principle. The primary outcome and dichotomous secondary outcomes of treatment arms will be compared by means of Chi-squared tests and odds ratios with 95% confidence intervals. Secondary outcomes measured on interval scales will be compared by means of t-tests, Welch-tests or Mann-Whitney test as appropriate, depending on whether test assumptions (particularly normal distribution and variance homogeneity) are met. Data will be checked for normal distribution and variance homogeneity prior to these analyses. Secondary outcomes measured on ordinal scales will be compared by means of Mann-Whitney U-tests. Reporting will be consistent with CONSORT guidelines. Statistical analyses will be performed with standard statistical software such as SPSS (IBM Corp., Armonk, NY), SAS (SAS Institute Inc., Cary NC) or R (R Core Team, 2017).

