#### Sample size:

The sample size calculation is based on the primary outcome of the incidence of hypoxemia defined as a peripheral oxygen saturation of  $\leq 90\%$  after inducing deep sedation while performing endoscopy.

The incidence of the primary outcome was assumed to be 30% in nasal oxygen insufflation group and 10% in the nasal continuous positive airway pressure group. A total sample size of 158, i.e., 79 patients per group, is required to achieve 90% power in the detection of a difference of 20% between the group incidences at a significance level of 0.05 using a two-sided test of proportions. It is assumed that all patients stay within their treatment group within the observational period.

The randomization and division in subgroup “nasal continuous positive airway pressure” and “nasal oxygen insufflation” will occur prior to study entry. The entire

collective will be divided into 2 populations and the allocation sealed in envelopes. The envelope will only be opened directly before the study so that investigator bias can be minimized.

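### Do the unnamed start and stop of the primary-outcome window, and airway rescue before SpO2 reaches 90%, call for a change to the plan?

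*Combined protocol and SAP*

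**What the plan says.** Under Primary outcome, the protocol counts SpO2 of 90% or lower registered by the monitoring system "after inducing deep sedation while under endoscopy intervention". The Sample size section repeats the definition with almost the same bounds: "after inducing deep sedation while performing endoscopy". Section 6 describes propofol given "until a MOAA/S Score of 1-2 is reached", but as a sedation target; neither statement of the outcome refers to it. Section 6 also provides for continuous SpO2 monitoring and for recording procedure length.

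Airway rescue is a separate secondary outcome: "Incidence of need for airway intervention (mask ventilation, intubation, interruption"). Its timing relative to SpO2 is not mentioned.

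Section 7 sets the analysis on an intention-to-treat basis: "The primary outcome and dichotomous secondary outcomes of treatment arms will be compared by means of Chi-squared tests and odds ratios", with 95% confidence intervals. It lists no sensitivity analysis. On protection against bias, the Sample size section says: "The envelope will only be opened directly before the study so that investigator bias can be minimized". That is concealment of allocation; no blinding after the envelope is opened is described.

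**The concern.** Two things look unsafe.

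- **The window.** The outcome is binary, so a single low reading near the edge of the window can change a patient's status. Induction could be taken to end at the first bolus, at the target sedation score or at scope insertion. The procedure could be taken to end at scope removal or later. It is not stated whether readings during an interruption count. Two people could score the same trace differently.
- **Early rescue.** A patient who is mask-ventilated, intubated or has the procedure interrupted while SpO2 is still above 90%, and who never falls to 90% afterwards, is a non-event. If a team that knows the allocation intervenes earlier in one arm, that arm loses events for reasons of behaviour. The bias would favour CPAP if rescue came earlier under CPAP, and oppose it if rescue came earlier under nasal oxygen.

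At stake would be the error rate and power of the primary comparison.

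**Working it through.** **Inputs from the Sample size section.** Assumed event rates of 30% under nasal oxygen and 10% under CPAP; two-sided 0.05; 90% power; 79 per group.

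**The plan's own figure.** With unpooled variance, n = (1.960 + 1.282)² × (0.3×0.7 + 0.1×0.9) / 0.20² = 10.507 × 0.30 / 0.04 = 78.8, rounded up to 79 per group and 158 in all. The stated size is reproduced. Exact binomial enumeration of the uncorrected chi-squared test gives 90.2% power at 79 per group.

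**Effect of early rescue.** Let f be the share of would-be events in an arm that early rescue prevents, so the observed rate is p × (1 − f). The documents give no f; all values below are assumptions. For scale, 30% of 79 is 23.7 expected events, so f of 10%, 20% or 30% removes about 2.4, 4.7 or 7.1 of them.

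No true effect, 30% in both arms without rescue:

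| f in the two arms | Observed rates | Chance of p < 0.05 |
|---|---|---|
| equal: 0, 10% or 20% | 30/30, 27/27, 24/24 | 5.1% each |
| 10% and 20% | 27/24 | 7.3% |
| 20% and 30% | 24/21 | 7.5% |
| 10% and 30% | 27/21 | 14.5% |
| 0 and 10% | 30/27 | 7.1% |
| 0 and 20% | 30/24 | 13.8% |
| 0 and 30% | 30/21 | 25.8% |

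True 30% v 10%:

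| f, oxygen / CPAP | Observed rates | OR | Power |
|---|---|---|---|
| 0 / 0 | 30/10 | 0.26 | 90.2% |
| 10% / 10% | 27/9 | 0.27 | 86.3% |
| 20% / 20% | 24/8 | 0.28 | 81.1% |
| 20% / 10% | 24/9 | 0.31 | 74.4% |
| 10% / 20% | 27/8 | 0.24 | 90.7% |

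The fall from 90.2% to 74.4% is 15.8 points. Equal loss alone costs 90.2 − 86.3 = 3.9 points at 10% and 90.2 − 81.1 = 9.1 points at 20%. So roughly 4 to 9 of the 15.8 points come from having fewer events, not from a difference between arms. The reverse pattern moves power by 0.5 points.

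**Would a rescue-inclusive analysis repair it?** Take no true effect and count every rescued patient as an event. If all of them would have reached 90%, the comparison returns to 30% v 30% and 5.1%. If one arm also rescues 5% of those who would not have reached 90%, its rate is 0.30 + 0.70 × 0.05 = 33.5% and the test rejects in 7.8%. At 10% the rate is 0.30 + 0.70 × 0.10 = 37% and rejection is 15.7%. The added analysis inherits the same unblinded decisions.

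**What the planned data already allow.** Each patient has a hypoxemia status and an airway-intervention status. The 2 × 2 table of the two, by arm, identifies those rescued but never at or below 90%, which is the group in question.

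**Window.** The two statements of the outcome agree in substance, so the 30% and 10% assumptions and the analysed outcome refer to the same period. The reading itself comes from a device. A start and stop chosen without regard to allocation are the same for both arms.

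**The case for a change.** The strongest opposing case is that naming events and recording the time, reason and SpO2 of each intervention costs little, that timing not recorded may be lost, and that window rules chosen after the data are seen invite challenge. It adds that a device-recorded reading does not protect against differences in when the team acts, and that similar rescue frequencies in the two arms could hide different timing.

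Much of this stands as good practice. The bounds are verbal only, and a supportive analysis fixed in advance is more convincing than one chosen later. The cross-tabulation has a limit too: it does not give the reason for an interruption.

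What does not stand is the step to a defect. It is too strong to say that the plan could not show whether the result depends on rescue, since the 2 × 2 table goes most of the way. Nor is there one literal window to write in. If it closed at scope removal, an interruption with withdrawal could end it early. If it opened at the later of target sedation and scope insertion, a randomised patient who reaches only one of these, or neither, would have no window, which sits badly with intention-to-treat. Only the sponsor can say which events were meant.

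**Conclusion.** No change to the plan is needed. The missing start and stop events are a gap in detail that the trial team can fill sensibly, ideally in its working definitions before the data are analysed. Scoring a patient rescued above 90% as a non-event is correct under the stated definition, and accepting that outcome in a trial with no described blinding is a fair trade-off given a device-registered threshold and a separate rescue outcome.

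The possible distortion ranges from none (5.1% rejection with equal loss) through about 7.3% to 7.5% for a 10-point gap in f when both arms lose events, up to 25.8% if 30% of events are lost in one arm only. These figures rest wholly on assumed rescue fractions with no support in the documents, and the direction is unknown. A rescue-inclusive analysis would be an optional robustness check, not a correction. The sample size of 158, the primary outcome and the chi-squared analysis stand as written.

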#### *Secondary outcomes:*

- Duration of intervention (absolute)
- Duration of hypoxemia/Time until recovery ( $>90\%$ ) (absolute)
- Hypoxemic events per intervention
- Ratio of hypoxemia duration compared to procedure duration (relatively)
- Incidence of need for airway intervention (mask ventilation, intubation, interruption)
- Comparison between subgroups BMI 30+; 35+; 40+  $\text{kg/m}^2$

- Sedation score (Modified Observer Assessment of Alertness/Sedation)
- Continuous measurement of endtidal CO2 via the mask

## 6. Protocol

Patients will be randomized to nasal continuous positive airway pressure or nasal oxygen insufflation.

Patients randomized to nasal continuous positive airway pressure will receive a positive pressure between 3 and 10cm H2O depending on the type of endoscopy, and an oxygen flow rate of 6l/min. Patients randomized to nasal oxygen insufflation nasal oxygen will be started with a flow of 6L/min.

Deep sedation will be performed under surveillance of an anaesthesia-team (physician and nurse) using a propofol bolus of 1 mg/kg adjusted body weight, followed by a continuous propofol infusion of 4mg/kg/h (adjusted to lean body weight) (MacDonald JJ, Moore J, Davey V, Pickering S, Dunne T. The weight debate. *J Intensive Care Soc.* 2015 Aug;16(3):234-238. doi: 10.1177/1751143714565059), until a MOAA/S Score of 1-2 is reached (Kowalski R, Mahon P, Boylan G, et al. Validity of the modified observer's assessment of alertness/sedation scale (MOAA/S) during low dose propofol sedation: 3AP6-3. *Eur J Anaesthesiol.* 2007;24:26-27, DOI:10.1097/00003643-200706001-00097). If necessary, additional boluses of 20mg Propofol will be administered until the desired sedation depth is achieved. SpO2 and heart rate will be monitored continuously. Blood pressure will be monitored using upper-arm cuff oscillometry (3-minute intervals). Additional data collected from the medical record will include baseline SpO2, post-interventional SpO2, procedure length, and length of stay in the post anesthetic care unit (PACU).

## 7. Statistics

Descriptive analysis will be performed to describe patient characteristics and clinical data. The primary and secondary outcomes will be analysed according to the intention-to-treat principle. The primary outcome and dichotomous secondary outcomes of treatment arms will be compared by means of Chi-squared tests and odds ratios with 95% confidence intervals. Secondary outcomes measured on interval scales will be compared by means of t-tests, Welch-tests or Mann-Whitney test as appropriate, depending on whether test assumptions (particularly normal distribution and variance homogeneity) are met. Data will be checked for normal distribution and variance homogeneity prior to these analyses. Secondary outcomes measured on ordinal scales will be compared by means of Mann-Whitney U-tests. Reporting will be consistent with CONSORT guidelines. Statistical analyses will be performed with standard statistical software such as SPSS (IBM Corp., Armonk, NY), SAS (SAS Institute Inc., Cary NC) or R (R Core Team, 2017).

#### Sample size:

The sample size calculation is based on the primary outcome of the incidence of hypoxemia defined as a peripheral oxygen saturation of  $\leq 90\%$  after inducing deep sedation while performing endoscopy.

The incidence of the primary outcome was assumed to be 30% in nasal oxygen insufflation group and 10% in the nasal continuous positive airway pressure group. A total sample size of 158, i.e., 79 patients per group, is required to achieve 90% power in the detection of a difference of 20% between the group incidences at a significance level of 0.05 using a two-sided test of proportions. It is assumed that all patients stay within their treatment group within the observational period.

The randomization and division in subgroup “nasal continuous positive airway pressure” and “nasal oxygen insufflation” will occur prior to study entry. The entire

collective will be divided into 2 populations and the allocation sealed in envelopes. The envelope will only be opened directly before the study so that investigator bias can be minimized.

## 8. Abbreviations

ASA	American Society of Anaesthesiology
BMI	Body Mass Index
WHO	World Health Organisation
MOAA/S	Modified Observer Assessment of Alertness/Sedation
PBW	Predicted Body Weight males (kg) = $50 + [0.91 \times (\text{Height in cm} - 152.4)]$ females (kg) = $45.5 + [0.91 \times (\text{Height in cm} - 152.4)]$
IBW	Ideal Body Weight Male (kg): $50,0 \text{ kg} + 2,3 \text{ kg}^* (\text{cm} - 60)$ Female (kg): $45,5 \text{ kg} + 2,3 \text{ kg}^* (\text{cm} - 60)$
ABW	Adjusted Body Weight IBW + 0,4 * (actual body weight - IBW)
LBW	Lean Body Weight males (kg) = $(9270 \times \text{TBW}) / [6680 + (216 \times \text{BMI})]$ females (kg) = $(9270 \times \text{TBW}) / [8780 + (244 \times \text{BMI})]$

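### The printed ideal body weight formula mixes centimetres with inch constants, so the weight used for the propofol bolus comes out at about twice actual weight

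*Combined protocol and SAP*

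**What the plan says.** Section 6 (Protocol) starts deep sedation "using a propofol bolus of 1 mg/kg adjusted body weight", followed by a "continuous propofol infusion of 4mg/kg/h (adjusted to lean body weight"). If the target MOAA/S score is not reached, flat 20 mg boluses are added.

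Section 8 (Abbreviations) defines the weights:

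- ABW: "IBW + 0,4 * (actual body weight - IBW").
- IBW, men: "50,0 \text{ kg} + 2,3 \text{ kg}^* (\text{cm} - 60").
- IBW, women: "45,5 \text{ kg} + 2,3 \text{ kg}^* (\text{cm} - 60").
- PBW, men: "50 + [0.91 \times (\text{Height in cm} - 152.4"), with 45.5 in place of 50 for women.

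Section 8 is the only place in the document that defines ABW and IBW. No conversion of height to inches appears anywhere.

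**The concern.** IBW and PBW share their intercepts and describe nearly the same quantity, yet as printed they differ four- to five-fold for the same patient. An IBW near 300 kg is implausible for any adult. ABW is a weighted average of IBW and actual weight, so an inflated IBW pushes ABW above actual weight. That is the opposite of what an adjustment for obesity is for.

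The error matters because it sits in a dosing rule. Participants are ASA class 3 or higher and/or have a BMI of at least 30, and section 1 describes them as prone to airway obstruction and hypoxemia. The primary outcome is hypoxemia after induction of deep sedation. The only adjustment that section 6 spells out for the boluses is upward, and a bolus that is too large cannot be taken back. If the printed rule were followed, it could also move hypoxemia incidence in both arms away from the 30% and 10% assumed in section 7. If some staff followed it and others silently corrected it, the induction dose would not be standardised.

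**Working it through.** **Inputs.** The formulas come from section 8 and the bolus from section 6. The plan gives no worked patient, so the heights and weights below are assumptions chosen to suit the eligible population. H is height in cm and W is actual weight in kg.

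- IBW as printed = 50 (men) or 45.5 (women) + 2.3 × (H − 60)
- PBW = 50 or 45.5 + 0.91 × (H − 152.4)
- ABW = IBW + 0.4 × (W − IBW) = 0.6 × IBW + 0.4 × W
- Bolus = 1 mg × ABW

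**Step 1: where the constants come from.** 60 in × 2.54 = 152.4 cm, and 2.3 kg per inch ÷ 2.54 = 0.906 kg per cm, which rounds to 0.91. The PBW line is therefore the IBW line with inches converted to centimetres. The IBW line keeps the inch constants but labels height in cm.

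**Step 2: two patients.**

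Man, 170 cm, 110 kg (BMI 38):
- IBW = 50 + 2.3 × 110 = 303.0 kg; PBW = 50 + 0.91 × 17.6 = 66.0 kg
- ABW as printed = 0.6 × 303.0 + 0.4 × 110 = 225.8 kg
- ABW from PBW = 0.6 × 66.0 + 0.4 × 110 = 83.6 kg

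Woman, 160 cm, 90 kg (BMI 35):
- IBW = 45.5 + 2.3 × 100 = 275.5 kg; PBW = 45.5 + 0.91 × 7.6 = 52.4 kg
- ABW as printed = 0.6 × 275.5 + 0.4 × 90 = 201.3 kg
- ABW from PBW = 0.6 × 52.4 + 0.4 × 90 = 67.4 kg

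| Patient | IBW / PBW | Printed ABW / actual weight | Printed ABW / PBW-based ABW |
|---|---|---|---|
| Man | 303.0 / 66.0 = 4.6 | 225.8 / 110 = 2.05 | 225.8 / 83.6 = 2.7 |
| Woman | 275.5 / 52.4 = 5.3 | 201.3 / 90 = 2.24 | 201.3 / 67.4 = 3.0 |

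At 1 mg/kg, the boluses as printed are about 226 mg and 201 mg, against about 84 mg and 67 mg.

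**Step 3: range.** Printed ABW divided by actual weight equals 0.4 + 0.6 × IBW/W. Over heights 160–180 cm, weights 90–150 kg and both sexes:

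- Lowest (woman, 160 cm, 150 kg): 0.4 + 0.6 × 275.5/150 = 1.50
- Highest (man, 180 cm, 90 kg; IBW = 50 + 2.3 × 120 = 326): 0.4 + 0.6 × 326/90 = 2.57

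Over the same grid, printed ABW is 2.4 to 3.0 times the PBW-based ABW.

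For a 170 cm man the multiple of actual weight by BMI is:

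| BMI | 25 | 30 | 35 | 40 | 50 | 60 |
|---|---|---|---|---|---|---|
| Printed ABW / actual | 2.92 | 2.50 | 2.20 | 1.97 | 1.66 | 1.45 |

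The BMI 25 column is relevant because a non-obese patient of ASA class 3 or higher can be enrolled. Printed ABW exceeds actual weight whenever printed IBW does, which for a 170 cm man means at any weight below 303 kg.

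**Step 4: check of the correction.** Entering height as H/2.54, a 170 cm man has IBW = 50 + 2.3 × (66.93 − 60) = 65.9 kg, against a PBW of 66.0 kg. A 170 cm woman has 61.4 kg against 61.5 kg. The two entries then agree.

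**The case against.** The strongest reply is that this is a visible slip in an abbreviations list, with no demonstrated consequence.

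- **It would be noticed.** An IBW of 300 kg is plainly wrong, the PBW entry beside it gives about 66 kg, and an anaesthesia physician and nurse supervise sedation with continuous SpO2 monitoring. This makes literal use less likely, and the doses actually given are unknown. It does not repair the written rule. Relying on staff to disregard a protocol dose is not a safeguard.
- **The scope is narrow.** Only the initial bolus uses ABW. The infusion uses lean body weight, whose formula does not contain IBW, and the top-up boluses are flat. This stands.
- **The comparison is not biased.** Both arms use the same formula, and neither the analysis nor the sample size calculation takes it as an input. This also stands. Any effect on the incidence of hypoxemia is conditional on literal use, and the documents do not quantify it.
- **The printed line may be incomplete.** A division by 2.54 could have been lost when the PDF was converted to text. That is unlikely: the male and female lines agree, the adjacent PBW lines came through cleanly, and nothing is marked as missing. It can be settled by looking at the PDF.

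None of these points defends the formula as printed.

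**Conclusion.** The concern holds: the IBW entry is wrong as written, and the document's own PBW entry shows it. At ordinary adult heights IBW comes out near 300 kg. The dosing weight for the bolus is then about twice actual weight for a typical obese patient (1.5 to 2.6 times over the heights and weights examined) and 2.4 to 3.0 times the PBW-based value. About twice is a mid-range figure: the multiple is larger in leaner patients and smaller at extreme BMI.

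These figures assume that the formula is applied literally to patients of the assumed sizes. They show what the protocol instructs, not what was given. The correction is essential because this is the protocol's only printed definition of the weight that sets a sedative bolus in high-risk patients.

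**What to change.** Correct the IBW entry in section 8 so that it agrees with PBW. Either write the height term as (height in cm/2.54 − 60) and keep the 2.3, or use the PBW coefficient and offset. State the height unit explicitly for both sexes, and have the responsible clinicians confirm the entry.

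Then check any dosing worksheet or calculator that uses ABW. In section 6 the bolus is the only quantity affected. Establish which formula was used for patients already treated, and report any who were dosed from the printed line. No change to the dose per kg is proposed here.

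The cost is a one-line protocol correction, a worksheet check and, if recruitment has begun, a look at the recorded boluses. The sample size and the analysis do not change.
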